8.3.3 Causality Collection

The investigator should assess causal relationship between study treatment and each AE, and answer 'yes' or 'no' to the question 'Do you consider that there is a reasonable possibility that the event may have been caused by the study treatment?'

For SAEs, causal relationship should also be assessed for other medication and study procedures. Note that for SAEs that could be associated with any study procedure the causal relationship is implied as 'yes'.

A guide to the interpretation of the causality question is found in Appendix B to the protocol.

8.3.4 Adverse Events Based on Signs and Symptoms

All AEs spontaneously reported by the patient or care provider or reported in response to the open question from the study site staff: 'Have you/the patient had any health problems since the previous visit/you were last asked?', or revealed by observation will be collected and recorded in the eCRF. When collecting AEs, the recording of diagnoses is preferred (when possible) to recording a list of signs and symptoms. However, if a diagnosis is known and there are other signs or symptoms that are not generally part of the diagnosis, the diagnosis and each sign or symptom will be recorded separately.

8.3.5 Adverse Events Based on Examinations and Tests

The results from the protocol mandated laboratory tests, vital signs, physical examinations, ECGs, and echocardiograms/MUGA scans will be summarised in the CSR.

Deterioration as compared to baseline in protocol-mandated laboratory values and vital signs should therefore only be reported as AEs if they fulfil any of the SAE criteria, are the reason for discontinuation of treatment with the study treatment or are considered to be clinically relevant as judged by the investigator (which may include but not limited to consideration as to whether treatment or non-planned visits were required or other action was taken with the study treatment, eg, dose adjustment or study treatment interruption).

If deterioration in a laboratory value/vital sign/physical examination/ECG/echocardiogram/MUGA is associated with clinical signs and symptoms, the sign or symptom will be reported as an AE and the associated laboratory result/vital sign/physical examination/ECG/echocardiogram/MUGA will be considered as additional information. Wherever possible the reporting investigator uses the clinical, rather than the laboratory term (eg, anaemia versus low haemoglobin value). In the absence of clinical signs

or symptoms, clinically relevant deteriorations in non-mandated parameters should be reported as AE(s).

Deterioration of a laboratory value, which is unequivocally due to disease progression per RECIST 1.1, should not be reported as an AE/SAE.

Any new or aggravated clinically relevant abnormal medical finding at a physical examination as compared with the baseline assessment will be reported as an AE unless unequivocally related to the disease under study.

8.3.6 Hy's Law

Cases where a patient shows elevations in liver biochemistry may require further evaluation and occurrences of AST or ALT \geq 3 × ULN together with total bilirubin \geq 2 × ULN may need to be reported as SAEs. Please refer to Appendix E for further instruction on cases of increases in liver biochemistry and evaluation of Hy's Law.

8.3.7 Disease Progression

Disease progression can be considered as a worsening of a patient's condition attributable to the disease for which the study treatment is being evaluated. It may be an increase in the severity of the disease under study and/or increases in the symptoms of the disease. The development of new, or progression of existing metastasis to the primary cancer under study should be considered as disease progression and not an AE. Events, which are unequivocally due to disease progression, should not be reported as an AE during the study. If the disease progression worsens in terms of time-course or severity compared to what would normally be expected for that patient, or if the investigator considers that there was a causal relationship between treatment with the study medication(s) or protocol procedures and the disease progression, the event must be reported as an SAE/SUSAR.

8.3.8 New Cancers

The development of a new cancer should be regarded as an AE and will generally meet at least one of the serious criteria. New primary cancers are those that are not the primary reason for the administration of study treatment and are identified after the patient's inclusion in this study. They do not include metastases of the original cancer.

8.3.9 Deaths

All deaths that occur during the study treatment period, or within the protocol-defined follow-up period after the administration of the last dose of study treatment, must be reported as follows:

• Death clearly resulting from disease progression should be documented in the eCRF in the Statement of Death page. It should not be reported as an SAE.

- Where death is not due (or not clearly due) to progression of the disease under study, the AE causing the death must be reported as an SAE within 24 hours. It should also be documented in the Statement of Death page in the eCRF. The report should contain a comment regarding the co-involvement of PD, if appropriate, and should assign the main and contributory causes of death.
- Deaths with an unknown cause should always be reported as an SAE and documented in the Statement of Death page in the eCRF, but every effort should be made to determine a cause of death. A post-mortem may be helpful in the assessment of the cause of death, and if performed, a copy of the post-mortem results should be forwarded to AstraZeneca Patient Safety or its representative within the usual time frames.

Deaths occurring after the protocol-defined follow-up period after the administration of the last dose of study treatment should be documented in the Statement of Death page. If the death occurred as a result of an event that started after the defined follow-up period and the event is considered to be due to a late-onset toxicity to study treatment, then it should also be reported as an SAE.

8.3.10 Adverse Events of Special Interest

Adverse events of special interests are events of scientific and medical interest specific to the further understanding of durvalumab and ceralasertib safety profile and require close monitoring and rapid communication by the investigators to AstraZeneca. An AESI can be serious or non-serious. All AESIs will be recorded in the eCRF. Serious AESIs will be recorded and reported as per Section 8.3.12.

AESIs for durvalumab

Adverse events of special interest for durvalumab include but are not limited to events with a potential inflammatory or immune-mediated mechanism and which may require more frequent monitoring and/or interventions such as steroids, immunosuppressants and/or hormone replacement therapy. An immune-mediated AE is defined as an AESI that is associated with drug exposure and is consistent with an immune-mediated MoA and where there is no clear alternate aetiology.

If the investigator has any questions in regard to an event being an immune-mediated AE, the investigator should promptly contact the AstraZeneca clinical lead.

Adverse events of special interest/immune-mediated AE observed with anti-PD-(L)1/PD-1 agents such as durvalumab include pneumonitis, hepatitis, diarrhoea/colitis, intestinal perforation, endocrinopathies (hypo- and hyperthyroidism, adrenal insufficiency, hypophysitis/hypopituitarism and Type 1 diabetes mellitus), nephritis, rash/dermatitis, myocarditis, myositis/polymyositis, pancreatitis and rare/less frequent events (including, but

not limited to haematological events, neuromuscular toxicities [such as myasthenia gravis and Guillain-Barré syndrome], non-infectious encephalitis, non-infectious meningitis, pericarditis, rheumatological events, sarcoidosis, skin events, uveitis [and other events involving the eye] and vasculitis).

In addition, infusion-related reactions and hypersensitivity/anaphylactic reactions with a different underlying pharmacological aetiology are also considered AESIs.

More detailed guidelines for their evaluation and treatment are described in detail in the Dose Modification and Toxicity Management Guidelines (see the Annex document to this CSP). These guidelines have been prepared by the sponsor to assist the investigator in the exercise of his/her clinical judgement in treating these types of toxicities. These guidelines apply to AEs considered causally related to the study treatment/study regimen by the reporting investigator.

AESIs for ceralasertib

At present there are no AESIs defined for ceralasertib.

8.3.11 Safety Data to be Collected Following the Final Data Cut Off of the Study

See Section 6.7 for treatment after the final DCO and patient management.

For patients continuing to receive ceralasertib or ceralasertib plus durvalumab after the final DCO in the PTAP, no data collection is required except for reporting of non-serious AEs, SAEs, and special situations (ie, pregnancy, overdoses, medication error, and drug abuse and misuse) until the end of post-trial access or until consent has been withdrawn. All data after the final DCO and database closure will be recorded in the patient notes but will not be reported for the purposes of this study except for the safety data mentioned above.

All SAEs that occur in patients still receiving ceralasertib or ceralasertib plus durvalumab in the PTAP must be reported as detailed in Section 8.3.12.

After study completion, when EDC is closed and if an AE/SAE needs to be reported, paper AE/SAE form should be used.

8.3.12 Reporting of Serious Adverse Events

All SAEs have to be reported, whether or not considered causally related to the study treatment, or to the study procedure(s). All SAEs will be recorded in the eCRF during the study conduct.

After study completion, when EDC is closed and SAE needs to be reported, paper SAE form should be used.

If any SAE occurs in the course of the study, then investigators or other site personnel must inform the appropriate AstraZeneca representatives within 1 day ie, immediately but **no later than 24 hours** of when he or she becomes aware of it.

The designated AstraZeneca representative works with the investigator to ensure that all the necessary information is provided to the AstraZeneca Patient Safety data entry site within 1 calendar day of initial receipt for fatal and life-threatening events and within 5 calendar days of initial receipt for all other SAEs.

For fatal or life-threatening AEs where important or relevant information is missing, active follow-up will be undertaken immediately. Investigators or other site personnel will inform AstraZeneca representatives of any follow-up information on a previously reported SAE within 1 calendar day ie, immediately but **no later than 24 hours** of when he or she becomes aware of it.

Once the investigators or other site personnel indicate an AE is serious in the EDC system, an automated email alert is sent to the designated AstraZeneca representative.

If the EDC system is not available, then the investigator or other study site staff reports a SAE via secure method to the appropriate AstraZeneca representative. Investigators or other site personnel send relevant paper CRF modules by fax to the designated AstraZeneca representative.

The AstraZeneca representative will advise the investigator/study site staff how to proceed.

When the EDC is temporarily not accessible, the AstraZeneca Study Representative should confirm that the investigator/site personnel enter the SAE in the AstraZeneca EDC when access resumes.

For further guidance on the definition of a SAE, see Appendix B of the CSP.

For regulatory reporting requirements for SAEs, see Appendix A 1.

The reference document for definition of expectedness/listedness is the IB for the AstraZeneca IMPs.

8.3.13 Pregnancy

All pregnancies, including pregnancy in the partner of male patients, and outcomes of pregnancy, with conception dates following the first date of study treatment, should be reported to AstraZeneca.

8.3.13.1 Maternal Exposure

Women of childbearing potential are allowed to be included in this study. Should a pregnancy occur, the study treatment should be discontinued immediately, and the pregnancy reported to AstraZeneca.

Pregnancy itself is not regarded as an AE unless there is a suspicion that the study treatment under study may have interfered with the effectiveness of a contraceptive medication. All pregnancies should be collected and provided to the AstraZeneca Data Entry Site (DES) via PREGREP module in the eCRF. If an AE/SAE is associated with the pregnancy, AE/SAE eCRF modules should also be completed and sent to AstraZeneca DES. Congenital abnormalities/birth defects and spontaneous miscarriages should be reported and handled as SAEs. Elective abortions without complications should not be handled as AEs. The outcome of all pregnancies (spontaneous miscarriage, elective termination, ectopic pregnancy, normal birth or congenital anomaly/birth defect) should be followed up and documented even if the patient was discontinued from the study. The paper based PREGOUT form should be used to report the outcome of the pregnancy.

If any pregnancy occurs in the course of the study, then the investigator or other site personnel informs the appropriate AstraZeneca representatives within 1 day, ie, immediately but no later than 24 hours of when he or she becomes aware of it.

The designated AstraZeneca representative works with the investigator to ensure that all relevant information is provided to the AstraZeneca Patient Safety data entry site within 1 or 5 calendar days for SAEs (see Section 8.3.8) and within 30 days for all other pregnancies.

The same timelines apply when outcome information is available.

8.3.13.2 Paternal Exposure

Non-sterilised male patients who intend to be sexually active with a female partner of childbearing potential should refrain from fathering a child or donating or banking sperm for 6 months after the last dose of study treatment.

Pregnancy in a patient's partner(s) is not considered to be an AE. However, the outcome of all pregnancies (spontaneous miscarriage, elective termination, ectopic pregnancy, normal birth or congenital anomaly), occurring from the date of the first dose until 90 days after the last dose and as indicated by previous studies (preclinical and clinical) should, if possible, be followed up and documented in the medical record and provided to the AstraZeneca Patients Safety data entry site. Consent from the partner must be obtained before the information is collected and reported to AstraZeneca via the Pregnancy Report Form. For country-specific requirements for Belgium and France see Appendices K 1.1 and K 1.2, respectively.

Where the report of pregnancy in a patient's partner is received, prior to obtaining information about the pregnancy, the investigator must obtain the consent of the patient's partner. The local study team should adopt the Master Pregnant Partner Form in line with local procedures and submit it to the relevant Regulatory Authority/IRBs/IECs prior to use.

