5.3 Lifestyle Considerations

5.3.1 Contraception

Male patients:

Non-sterilised male patients (including males sterilised by a method other than bilateral orchidectomy, eg, vasectomy) who intend to be sexually active with male partners and women of non-child bearing potential must be using an acceptable method of contraception such as

male condom plus spermicide (condom alone in countries where spermicides are not approved) from the time of screening throughout the total duration of the study and for 1 week after the last dose of study treatment to prevent exposure to ceralasertib via the semen. Where a sexual partner of a male patient is a 'woman of childbearing potential' who is not using effective contraception, or who is already pregnant, then the male patient must use a condom plus spermicide (where approved), during the study and for a further 6 months after the last dose of study treatment to prevent pregnancy in a partner. Male patients should refrain from fathering a child or donating sperm from the start of dosing until 6 months after the last dose of study treatment, if there is a concern about damaging the developing foetus from drug in ejaculate. For country-specific requirements for Belgium and France see Appendices K 1.1 and K 1.2, respectively.

Periodic abstinence, the rhythm method, and the withdrawal method are not acceptable methods of contraception.

Vasectomised males are considered fertile and should still use a male condom plus spermicide as indicated above during the clinical study.

Female partners (of childbearing potential) of male patients must also use a highly effective method of contraception throughout this period (Table 7).

Female patients:

- Women not of childbearing potential are defined as women who are surgically sterile (ie, complete hysterectomy, bilateral oophorectomy, or bilateral salpingectomy), or who are postmenopausal.
- Women will be considered postmenopausal if they have been amenorrhoeic for 12 months prior to the planned date of randomisation without an alternative medical cause. The following age-specific requirements apply:
 - Women < 50 years old would be considered postmenopausal if they have been amenorrhoeic for 12 months or more following cessation of all hormonal replacement therapy and if they have luteinising hormone and follicle-stimulating hormone levels in the post-menopausal range for the institution.

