- Patients must be informed that their participation is voluntary and they are free to refuse to participate and may withdraw their consent at any time and for any reason during the study. Patients or their legally authorised representative will be required to sign a statement of informed consent that meets the requirements of 21 CFR 50, local regulations, ICH guidelines, Health Insurance Portability and Accountability Act (HIPAA) requirements, where applicable, and the IRB/IEC or study centre.
- The medical record must include a statement that written informed consent was obtained before the patient was enrolled in the study and the date the written consent was obtained. The authorised person obtaining the informed consent must also sign the ICF.
- Patients must be re-consented to the most current version of the ICF(s) during their participation in the study.
- A copy of the ICF(s) must be provided to the patient or the patient's legally authorised representative.

For country-specific requirements for Germany see Appendix K 1.3.

Patients who are rescreened are required to sign a new ICF.

The ICF will contain a separate section that addresses and documents the collection and use of any mandatory and/or optional human biological samples. The investigator or authorised designee will explain to each patient the objectives of the analysis to be done on the samples and any potential future use of the samples and the data obtained from these samples. Patients will be told that they are free to refuse to participate in any optional samples or the future use and may withdraw their consent at any time and for any reason during the retention period.

If a patient's partner becomes pregnant within 90 days after the last dose of durvalumab, the partner is asked to sign the "Adult Study Informed Consent Form for Pregnant Partners of Study Patients" and provide information about the pregnancy accordingly.

A 4 Data Protection

- Patients will be assigned a unique identifier by Trusted Third Party contracted by the Sponsor or by a Principal Investigator. Any patient records or datasets that are transferred to AstraZeneca will contain the identifier only; patient names or any information which would make the patient identifiable will not be transferred.

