After study treatment discontinuation, all patients will be followed up for safety assessments 30 days after their last dose of study treatment for ceralasertib monotherapy or 90 days after last dose of study treatment for ceralasertib and durvalumab combination. Patients will also be followed for survival status and post discontinuation anti-cancer therapies. A urine pregnancy test must also be performed for WOCBP 6 months after last dose of study treatment (ceralasertib monotherapy or ceralasertib in combination with durvalumab). Additional assessments to be performed at the time of the safety follow up are detailed in the SoA (Section 1.3).

Section 8.3.13.2 (Paternal Exposure)

Revised text

Pregnancy in a patient's partner(s) is not considered to be an AE. However, the outcome of all pregnancies (spontaneous miscarriage, elective termination, ectopic pregnancy, normal birth or congenital anomaly), occurring from the date of the first dose until 180 days after the last dose and as indicated by previous studies (preclinical and clinical) should, if possible, be followed up and documented in the medical record and provided to the AstraZeneca Patients Safety data entry site. Consent from the partner must be obtained before the information is collected and reported to AstraZeneca via the Pregnancy Report Form.

K 1.2 Country-specific Requirements for France

Section 1.1 (Synopsis)

Revised text

After study treatment discontinuation, all patients will be followed up for safety assessments 30 days after their last dose of study treatment for ceralasertib monotherapy or 90 days after last dose of study treatment for ceralasertib and durvalumab combination. A urine pregnancy test must be performed for WOCBP at 6 months after their last dose of study treatment (ceralasertib monotherapy and ceralasertib in combination with durvalumab). All randomised patients in the main study and all patients in the biopsy sub study will be followed for survival status and post discontinuation anti-cancer therapies.

Revised table

Procedure	Screening a		Intervention period (28-day cycles) Post-intervention follow-up period													iod	Details in CSP section or appendix
	Scr		Cycl	es 1-2		Cycle 3 C4-onwards						Safety follow-up (# of days after last dose) the state of the state					
Cycle Day	-21 to -1	Day 1	Day 7	Day 8	Day 15	Day 1	Day 7	Day 8	Day 1	Day 8	ntment of stud	30 days	60 days	90 days	6 months	Progression/Survival Follow-up (Q8W until 8 months, then Q12W)	

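### The 90-day limit on partner-pregnancy outcomes in 8.3.13.2 conflicts with the 6-month no-fathering period and the open-ended rule in 8.3.13, and Appendix A 3 ties partner consent to a drug the monotherapy arm never receives

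*Protocol*

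**What the plan says.** Protocol 8.3.13.2 (Paternal Exposure) deals with the same exposure in three paragraphs.

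- The first says that non-sterilised men with a partner of childbearing potential "should refrain from fathering a child or donating or banking sperm for 6 months after the last dose of study treatment".
- The second asks for outcomes of partner pregnancies "occurring from the date of the first dose until 90 days after the last dose and as indicated by previous studies (preclinical and clinical"), with the partner's consent obtained before information is collected.
- The third says that, when a partner pregnancy is reported, "prior to obtaining information about the pregnancy, the investigator must obtain the consent" of the partner. It sets no limit by time or arm.

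The surrounding text uses other limits:

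- 8.3.13 wants all pregnancies reported to the sponsor, "including pregnancy in the partner of male patients, and outcomes of pregnancy, with conception dates following the first date of study treatment". No end date is given.
- 8.3.13.1 says maternal outcomes "should be followed up and documented even if the patient was discontinued from the study", again with no cap.
- 5.3.1 requires condom use where a partner of childbearing potential lacks effective contraception or is already pregnant, "during the study and for a further 6 months after the last dose of study treatment to prevent pregnancy in a partner".
- Appendix K 1.1 (Belgium) rewrites the second paragraph of 8.3.13.2 to cover pregnancies "occurring from the date of the first dose until 180 days after the last dose". Appendix K 1.2 (France) extends it to 6 months plus five half-lives.
- Appendix A 3 provides that if a patient's partner "becomes pregnant within 90 days after the last dose of durvalumab, the partner is asked to sign" the pregnant-partner consent form.

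**The concern.** A site has two instructions of different length for the same event. Read literally, the second paragraph of 8.3.13.2 lets outcome follow-up lapse for a partner pregnancy that begins in months 4 to 6 after the last dose. The protocol itself treats that period as one of concern, because 5.3.1 links the 6-month rule to possible harm to a foetus from drug in ejaculate. Pregnancies that occur despite that precaution are the ones whose outcomes are most informative.

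The consent trigger in Appendix A 3 adds a second problem. It counts from a durvalumab dose, so it has no start date for a man in the ceralasertib-alone arm. Consent comes before any information is collected, so a site working from Appendix A 3 alone might not begin the process for that arm.

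Both points still apply although recruitment has ended, because they govern patients on treatment or in follow-up.

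**Working it through.** No sample-size, power or error-rate figure is involved. The check compares the stated time ranges and subtracts them.

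**Inputs**

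| Place in the protocol | Rule | Limit after last dose |
|---|---|---|
| 8.3.13.2, first paragraph | No fathering of a child | 6 months, study treatment |
| 5.3.1, male patients | Prevent pregnancy in a partner | 6 months, study treatment |
| 8.3.13 | Report partner pregnancies and outcomes | None |
| 8.3.13.2, second paragraph | Outcomes of partner pregnancies | 90 days |
| Appendix K 1.1, Belgium | Same paragraph, revised | 180 days |
| Appendix K 1.2, France | Same paragraph, revised | 6 months plus 5 half-lives (2.5 days) |
| Appendix A 3 | Partner asked to sign consent form | 90 days, durvalumab only |
| 8.3.13.2, third paragraph | Partner consent on any report | None |

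Table 1 of the Schedule of Activities labels its last safety visit both 180 days and 6 months, so 6 months is taken as 180 days.

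**What the 90 days limits.** The phrase governs when the pregnancy occurs. It does not say how long an included pregnancy is followed.

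**Gap against the protocol's own 6-month period**

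- 180 − 90 = 90 days, that is, days 91 to 180.
- 90 / 180 = one half of the protected period.

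**Gap against the country versions**

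- Belgium: 180 − 90 = 90 days.
- France, if 2.5 days is the whole addition: 180 + 2.5 = 182.5, and 182.5 − 90 = 92.5 days.
- France, if 2.5 days is one half-life: 180 + 5 × 2.5 = 192.5, and 192.5 − 90 = 102.5 days. The French wording allows either reading.

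**Consent trigger by arm.** Section 4.1 gives Arm 2 ceralasertib alone and does not permit crossover. A last durvalumab dose is therefore undefined for that arm, planned at about 50 patients. The Belgian and French sections revise 8.3.13.2 but list no change to Appendix A 3. In those two countries the consent trigger stays at 90 days after durvalumab, while the outcome range is at least 180 days.

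**After the proposed change.** With the range set to at least 180 days, the uncovered part of the 6-month period falls from 90 days to 0.

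**The case against.** The strongest reply is that the governing text already covers these pregnancies. Section 8.3.13 asks for all partner pregnancies and outcomes conceived after first treatment, in either arm and with no end date. The third paragraph of 8.3.13.2 requires partner consent on any report. For patients treated after the final data cut-off, 8.3.11 separately keeps pregnancy reportable until post-trial access ends. The 90-day phrase also carries an open-ended qualifier about previous studies.

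Much of this stands. A reader might infer that partner pregnancies after day 90 are not collected at all, or that monotherapy partners have no route to consent. The documents support neither inference: 8.3.13 covers the first and 8.3.13.2 the second. The reply does not make the texts agree. The qualifier supplies no other end date, and a site following the second paragraph of 8.3.13.2 to the letter would fall short of 8.3.13.

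A reader might also infer from exclusion criterion 29, which still asks for birth control for only 1 month (monotherapy) or 3 months (combination), that patients could enter on a shorter commitment. This does not hold. Inclusion criterion 16 requires 6 months, all inclusion criteria must be met, and the summary of changes says recruitment has ended.

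Finally, it can be objected that rewording may find few extra cases. That is fair. Monotherapy has one scheduled safety visit, at 30 days. The 8-weekly survival contacts in 7.1.3 may be made with family or the patient's current physician, and nothing shows that they ask about partner pregnancy.

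**Conclusion.** The point holds as conflicting safety-collection wording. The global outcome range in 8.3.13.2 is 90 days shorter than the section's own no-fathering period and than the Belgian version, 92.5 or 102.5 days shorter than the French version, and at odds with the open-ended parent rule. The Appendix A 3 trigger names a drug that one arm does not receive and differs from the consent rule in 8.3.13.2.

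The day counts assume that 6 months is 180 days. How many partners are affected cannot be worked out from the protocol. No efficacy endpoint, safety analysis set or planned analysis changes. It deserves correction because it concerns live safety reporting and the remedy is simple, but it does not put the trial's conclusions at risk.

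**What to change.** In global 8.3.13.2, replace the 90-day limit with a range of at least 6 months from the final dose of study treatment, or drop the range and refer to 8.3.13. Leave the Belgian and French text in Appendix K as it is: those are country-specific requirements, and nothing in the protocol shows that they could be withdrawn.

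In Appendix A 3, replace the durvalumab clause with a trigger that applies whenever a partner pregnancy is reported under 8.3.13, for either regimen.

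Bringing exclusion criterion 29 into line at 6 months is optional tidying with no current effect.

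The cost is a wording amendment and a check of the pregnant-partner form, with the IRB/IEC and applicable Regulatory Authority approval described in Appendix A 1. No visit or test has to be added for the texts to agree. Reporting will still depend on the site learning of the pregnancy, because no scheduled contact in months 4 to 6 is shown to ask about it in the monotherapy arm.
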